3.2.6 Organ Function Requirements

All subjects must have adequate organ function defined below when starting on protocol.

3.2.6.1 Hematologic Function:

- a. Hemoglobin: ≥ 8.0 gm/dl (may transfuse PRBCs)
- b. ANC: $\geq 750/\text{mm}^3$, Must be at least 7 days after last dose of growth factor
- c. Platelet Count: $\geq 50,000$ (transfusion independent; ≥ 7 days from last transfusion)

3.2.6.2. Renal Function defined as:

Creatinine clearance/GFR > 70 cc/min/1.73 m² or

Serum creatinine based on age/gender as follows:

Age	Maximum Serum Creatinine (mg/dL)	
	Male	Female
1 month to < 6 months	0.4	0.4
6 months to < 1 year	0.5	0.5
1 to < 2 years	0.6	0.6
2 to < 6 years	0.8	0.8
6 to < 10 years	1	1
10 to < 13 years	1.2	1.2
13 to < 16 years	1.5	1.4
≥ 16 years	1.7	1.4

The threshold creatinine values in this Table were derived from the Schwartz formula for estimating GFR (Schwartz et al. J. Peds, 106:522, 1985) utilizing child length and stature data published by the CDC.

3.2.6.3 Liver Function:

- a. Total bilirubin \leq 1.5 x ULN for age, AND
- b. SGPT (ALT) < 2.5x ULN
- c. SGOT (AST) < 2.5x ULN

3.2.6.4 Pulmonary Function:

No evidence of dyspnea at rest, no exercise intolerance, and a pulse oximetry \geq 94% if there is clinical indication for determination.

3.2.6.5 Coagulation Function:

Normal PT and PTT at enrollment per institutional range

3.2.6.6 Reproductive Function:

Due to potential teratogenic effects of (poly-ICLC), negative serum beta-HCG in females, and agreement to the use of effective contraception in males and females of childbearing potential, **IS REQUIRED**.

3.3 Exclusion Criteria

- 3.3.1. Pregnant or lactating females. Women of childbearing age will agree to use contraception during the protocol.
- 3.3.2 Patients receiving other experimental immunotherapy.
- 3.3.3 Patients may not have fever (38.5°C) within 7 days of enrollment.

3.3.4 No concurrent XRT or chemotherapy is allowed.

3.3.5 Patients who, in the opinion of the investigator, may not be able to comply with the safety monitoring requirements of the study.

3.4 Regulatory

3.4.1 Informed Consent

All subjects and/or their parents or legal guardians must sign a written informed consent document. Written assent will be obtained from patients per institutional guidelines.

3.4.2 Protocol Approval

All institutional, FDA, and NCI requirements for human studies must be met including institutional IRB approval of the protocol.

4.0 Study Treatment

4.1 Treatment Schedule

Children will receive poly-ICLC 20 mcg/kg/dose twice weekly IM (using Monday/Thursday or Tuesday/Friday schedule if possible). The first 2 doses will be administered in the clinic under supervision.

Vital signs will be monitored every 30 minutes for 2 hours after the first dose. For all subsequent doses administered at home, a temperature log will be kept to document the temperature prior to study drug administration and at two separate time points after each of the 8 doses of study drug in cycle 1. One temperature reading will be assessed between hours 2-4 after study drug administration and one temperature reading will be assessed at 12 hours after study drug administration. After cycle 1, temperature will only be monitored on an as needed basis, such as if the subject is not feeling well. Subjects or their parents will be instructed to use a log to record the temperature monitored at home and any fever should be reported to the study team. In some cases, at the discretion of the research team, subject or parent will be allowed, after appropriate teaching, to administer the study drug at home. The study drug will be dispensed to the subject/parent by the research pharmacy. The study drug will be dispensed in vials along with labeled dose syringes in order to minimize errors in dosing.

Total length of treatment will be two years. Each cycle will be 28 days in length. If subjects demonstrate a response to therapy (see section 7.0), treatment may be continued beyond two years at the discretion of the principal investigator and pending drug availability. For statistical analysis of toxicity, subjects will be divided into two separate cohorts (those with NF1 and those without NF1). The subjects in each of these cohorts will be treated and monitored identically throughout treatment.

Subjects who travel to the coordinating or enrolling sites for protocol therapy may return home to the care of their primary pediatric oncologist after completing cycle 1 of therapy for standard of care management at the discretion of the study physician/committee. Subjects will be seen and monitored by their primary treating oncologist at the start of each cycle. For those subjects, a 3 month supply of study drug will be dispensed to the subject/family from their enrolling site. The enrolling site will continue to see the subject every 3 months for evaluation and will remain responsible for continued data capture of all required information.

4.2: Dose modifications based on Toxicity

If AST/ALT > 10x ULN while on study, Poly ICLC will be discontinued until the AST/ALT are < 5x ULN; the study drug will then be restarted at 20 mcg/kg/dose twice weekly (the initial dose).

If AST/ALT > 10x ULN for a second time, hold study drug until values < 2.5x ULN; then restart drug at the reduced dose of 10 mcg/kg/dose twice weekly.

Study drug will be stopped and subject will be off treatment for toxicity if AST/ALT do not decrease to < 5x ULN during the first episode and <2.5x ULN at second episode when drug is held for three weeks.

For the NF 1 cohort, consider restarting drug again at 5 mcg/kg/dose twice weekly if toxicities recur at the prior reduced dose of 10mcg/kg/dose.

For all other grade 3 or grade 4 toxicities the same dose modifications will be followed. The study drug will be held until resolution of these toxicities to ≤ grade 1. If the toxicity is not resolved within 3 weeks of the last dose of the study drug administration the subject will be taken off protocol therapy.

4.3: Concomitant Therapy

Corticosteroids and anticonvulsants may be given as indicated clinically. However, if the dose of steroids is increased while on therapy, MRI must be performed to rule out disease progression. Acetaminophen may be given as needed to control poly-ICLC side effects. A non-P450 inducing anticonvulsant will be used while on this study (see Appendix 3).

Radiotherapy may not be given while on study to the lesions being utilized as measurable disease in order to assess response. Patients may enter on study after completion of involved field radiation therapy, however at least 8 weeks should elapse after radiation, and scans should show residual disease prior to entry on study. Chemotherapy is not allowed.

Antibiotics, blood products and general supportive care measures may be used as clinically indicated. Appropriate antibiotics, blood products, antiemetics, fluids, electrolytes and general supportive care are to be used as necessary and as per institutional guidelines. Given the risk of intratumoral hemorrhage with thrombocytopenia, a platelet transfusion should be considered if the platelet count is < 25,000/mm³. Higher transfusion parameters may be used if clinically indicated. All blood products will be leukocyte depleted and irradiated to prevent graft-versus-host disease.

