8.0 CRITERIA FOR REMOVAL FROM PROTOCOL THERAPY AND OFF STUDY CRITERIA

8.1 Criteria for Removal from Protocol Therapy

a. Progressive disease

Note: Transient enlargement of enhancing disease with subsequent shrinkage has been reported during poly-ICLC treatment. Because of this, if the patient has progressive disease by the conventional definition above but does not have unacceptable progression by the definitions below, the treating physician and patient have the options of continuing poly-ICLC treatment on this protocol or of discontinuing treatment.

b. Criteria for unacceptable progression: See definitions of tumor progression outlined in section 7.1.3

1. >50% increase in the product of the three perpendicular diameters of initial tumor relative to the initial baseline measurement – LxWxT (current can) $> 1.5 \times$ LxWxT (initial scan), or the development of any new sites of disease independent of the response of the initial tumor. Post radiation changes are often seen on post-treatment imaging studies, so that classification of a patient as having progressive disease may require several serial MRI's if the child has received radiation within the preceding 12 months.

2. Unacceptable worsening of neurological symptoms that cannot be controlled with corticosteroids.

3. Any other radiological or clinical evidence of worsening to the extent that the treating physician feels it is not in the patient's best interest to continue poly-ICLC.

c. Physician determines it is in patient's best interest.

- d. Patient and/or parent/guardian refusal to continue or inability to comply with protocol
- e. Grade 3 or 4 toxicity that does not resolve to Grade 1 within three weeks after interruption of therapy, or recurrent grade 3 or 4 toxicity at a reduced dose level (see section 4.2).

Note: If final analysis confirms a beneficial effect of poly-ICLC, and/or if tumor recurs after withdrawal from poly-ICLC at the end of the 2-year prescribed treatment period, participating subjects may be offered continued treatment with poly-ICLC (subject to drug availability at that time).

- f. Completion of planned therapy.

Subjects who are off protocol therapy are to be followed until they meet the criteria for Off Study (see below). Follow-up data will be required, unless consent is withdrawn, every 3 months for the first year, every 4 months for the second year, every 6 months for the third year, and then yearly thereafter

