- Association of baseline levels of proteins (such as OAS, interferon, PKR, phosphorylation state of eIF2a, p21^{waf-1}) in serum, PBMC and/or cerebrospinal fluid with progression free survival.
- Association of changes in levels of proteins (such as OAS, interferon, PKR, phosphorylation state of eIF2a, p21^{waf-1}) serum, PBMC and/or cerebrospinal fluid from baseline with tumor response status at 6 months after treatment with Poly-ICLC.
- Association of changes in levels of proteins (such as OAS, interferon, PKR, phosphorylation state of eIF2a, p21^{waf-1}) in serum, PBMC and/or cerebrospinal fluid from baseline with progression free survival.

9.1: Study Design and Justification of Sample size

9.1.1 This is a single arm study, to determine the radiographic progression free survival (PFS) rate to poly-ICLC in the treatment of children with recurrent or progressive low grade gliomas. The primary endpoint is the progression free survival status at 6 months (PFS6) after starting therapy. The tumor response categories will include complete response, partial response, stable disease or progressive disease, as assessed according to section 7.1.2.

Simon's optimal two-stage design will be used for this study (Simon, 1989). Suppose 50% is the uninteresting level, i.e., if the PFS6 rate is $\leq 50\%$, we will consider the new regimen as not promising. This 50% baseline response rate in the absence of treatment is from historical experience (this rate was also used by the Everolimus study which is a phase II study for recurrent or progressive LLG in children), also taking into account that this study patient population are more refractory. We will test the null hypothesis $H_0: p \leq 50\%$ against the alternative hypothesis $H_1: p > 75\%$, where p is the PFS6 rate. The two stage design proposed below will have 80% power to reject the null and conclude that the true response rate is above 50%, if the true response rate is $\geq 75\%$, at 5% significance level.

The study design can be described in detail as follows:

Stage 1: Fourteen subjects will be accrued; accrual will be held up until the PFS6 results for all the 14 subjects are known. The trial will be terminated at Stage 1 if ≤ 7 subjects have a PFS6 response; otherwise it continues to Stage 2. Note that any subject who goes off study early due to toxicity, will be counted as a non-response (an intent to treat analysis).

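### For an NF1 child with recurrent grade 3 or 4 toxicity at the reduced dose, sections 4.2 and 8.1e disagree on restart or removal; any effect on PFS6 is conditional

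*Combined protocol and SAP*

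**What the plan says.** **Section 4.2 (dose modification).** When AST/ALT first exceeds 10x ULN, "Poly ICLC will be discontinued until the AST/ALT are < 5x ULN", after which the child restarts at the initial dose. The second time the instruction is "hold study drug until values < 2.5x ULN", followed by a restart at a reduced dose. Treatment ends for toxicity "if AST/ALT do not decrease to < 5x ULN during the first episode and <2.5x ULN at second episode" with the drug held for three weeks. All other grade 3 or 4 toxicities follow the same steps, but must recover to grade 1 or lower within three weeks. One further step applies to one cohort only: "For the NF 1 cohort, consider restarting drug again at 5 mcg/kg/dose twice weekly if toxicities recur at the prior reduced dose of 10mcg/kg/dose".

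**Section 8.1e (removal from protocol therapy).** Two triggers are listed, for all subjects: "Grade 3 or 4 toxicity that does not resolve to Grade 1 within three weeks after interruption of therapy", and "recurrent grade 3 or 4 toxicity at a reduced dose level (see section 4.2").

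**Section 4.1.** Of the NF1 and non-NF1 cohorts: "The subjects in each of these cohorts will be treated and monitored identically throughout treatment".

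**Scoring.** Section 9.1.1 says that "any subject who goes off study early due to toxicity, will be counted as a non-response". Section 9.1.5 counts an event against the therapy when an endpoint cannot be assessed. Section 8.1 keeps children who are off protocol therapy in follow-up, every 3 months in the first year. The off-study reasons in 8.2 are death, loss to follow-up, entry into another therapeutic study and withdrawal of consent.

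**The concern.** Two investigators following the protocol correctly could act differently on the same child after recurrent severe toxicity: one removes the child under 8.1e, the other restarts under 4.2. Section 2.2 describes patients with neurofibromatosis-associated tumors as having more side effects on this drug, so the conflict falls on the cohort most likely to meet it. Under 4.1, children may also return to their primary oncologist after cycle 1 with a 3-month drug supply, so the rules can be applied outside the two study sites.

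The statistical stake is the primary count. The trial turns on 7 versus 8 of 14 at stage 1 and on 15 versus 16 of 23 at the end. If removal for toxicity is scored as a failure while continuation can be scored as a success, the choice between two conflicting passages could enter that count.

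**Working it through.** **1. NF1 recurrence.** Take an NF1 child whose grade 3 or 4 toxicity recurs at the reduced dose.

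| Section | Outcome | NF1 exception |
|---|---|---|
| 8.1e | listed reason for removal | none |
| 4.2 | a further restart may be considered | is itself NF1-only |

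The pointer in 8.1e to 4.2 sets no precedence, and 4.2 gives no criterion for the choice. Below grade 3 there is no conflict, because 8.1e covers only grades 3 and 4.

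**2. Section 4.1.** The NF1-only step in 4.2 is what departs from identical treatment of the cohorts.

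**3. AST/ALT.** Let L be the upper limit of Grade 1 in multiples of ULN. CTCAE 4.0 is cited in 10.2, but its limits are not printed, so L is an assumption. Let v be the value three weeks into a hold. By saying *all other*, 4.2 treats AST/ALT above 10x ULN as a grade 3 or 4 toxicity, so 8.1e applies to it.

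- First episode: 4.2 permits restart if v < 5; 8.1e removes if v > L. Contradiction for L < v < 5, which exists only if L < 5.
- Second episode: 4.2 stops treatment if v is not below 2.5; 8.1e removes if v > L. If L is 2.5 or more, 4.2 is at least as strict and both rules can be obeyed.
- Example L = 2.5: a first-episode child between 2.5x and 5x restarts under 4.2 and is removed under 8.1e.
- Example L = 5: no first-episode gap; 4.2 is stricter at the second episode.

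One limit cannot equal both 5x and 2.5x, so the rules are not aligned. Whether they contradict each other depends on L.

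**4. Path to PFS6.** PFS events are progression, recurrence, death and second malignancy (1.1.1 and 9.0); stopping the drug is not one. Removal changes the score only if all of these hold:

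- it falls before the 6-month assessment;
- the child is otherwise progression-free;
- either *off study* in 9.1.1 is read as off therapy, or the 6-month assessment is not done.

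The timing is possible. Six cycles are 6 × 28 = 168 days; two earlier holds of up to 21 days take at most 42, leaving 126 for a third episode.

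**5. The plan's own design figures.** Inputs from 9.1.1 and 9.1.4: p0 = 0.50, p1 = 0.75, stop if 7 or fewer of 14, success if 16 or more of 23.

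- Early stopping = P(X ≤ 7), X ~ Bin(14, 0.50): 60.5% (stated 61%).
- P(success) = sum over x = 8 to 14 of P(X = x) × P(Y ≥ 16 − x), Y ~ Bin(9, p): 80.2% at 0.75 (stated 80%) and 4.6% at 0.50 (within the stated 5%).

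The design reproduces.

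**6. One child rescored.** 1/23 = 4.3 points of PFS6; 15/23 = 65.2% and 16/23 = 69.6%. Fix one stage-1 child as s = 1 or s = 0 and leave the other 13 + 9 binomial. P(success) = sum over x with x + s ≥ 8 of P(Bin(13, p) = x) × P(Bin(9, p) ≥ 16 − x − s).

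| True rate of the others | Scored success | Scored failure | Difference |
|---|---|---|---|
| 75% | 83.7% | 69.5% | 14.2 points |
| 50% | 6.7% | 2.6% | 4.1 points |

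**7. How many children.** The documents give no rate of removal for toxicity. Section 2.3 reports no dose-limiting toxicity in 45 children at 20-30 mcg/kg twice weekly; the one-sided 95% upper limit is 1 − 0.05^(1/45) = 6.4%. Assume that a share k of otherwise progression-free children is removed before 6 months and scored as failures, so that p becomes p(1 − k):

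| k (assumed) | P(success), true 75% | P(success), true 50% |
|---|---|---|
| 0 | 80.2% | 4.6% |
| 2% | 75.1% | 3.8% |
| 5% | 66.6% | 2.7% |
| 6.4% | 62.3% | 2.3% |
| 10% | 51.3% | 1.5% |

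Here k covers every toxicity removal scored as failure. Children caught by the 4.2/8.1e conflict are only part of it, so the table sizes the scoring question, not the conflict alone.

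**The case against.** The strongest reply is that 8.1e itself refers to 4.2, so 4.2 can be taken as the specific rule and the NF1 step as a deliberate exception. The sentence in 4.1 follows an explanation of the cohorts for toxicity analysis and may describe only a common schedule. The NF1 step is permissive and names no grade. With two sites, a monthly joint review and a DSMB, divergent handling would probably be noticed. Few children should reach a third episode before 6 months. All of this limits the size of the problem, but none of it supplies the missing precedence. The 0/45 figure does not exclude grade 3 events either: section 2.2 reports a grade 3 low white count in one of four children with low-grade glioma.

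Three stronger readings are tempting and are not supported.

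- *Removal for toxicity is automatically a PFS6 failure.* Section 8.1 governs therapy and keeps the child in follow-up, 8.2 lists no toxicity reason, and 9.1.5 applies only when the endpoint cannot be assessed. On that wording a removed child can still count as progression-free. The uncertainty is real, though: the toxicity sentence in 9.1.1 has no matching route in 8.2, the table in 5.0 puts end of therapy and off study in one column, and MRI timing during follow-up after removal is not specified.
- *The AST/ALT limits contradict 8.1e whatever the grading table says.* If Grade 1 extends to 5x ULN, both rules can be obeyed.
- *Section 8.1e conflicts with 4.1.* It does not; it applies one rule to everyone.

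**Conclusion.** The protocol gives two incompatible instructions for an NF1 child with recurrent grade 3 or 4 toxicity at the reduced dose, and the NF1-only step does not fit 4.1 as worded. These two findings rest on the text alone. The AST/ALT recovery limits are misaligned with 8.1e; a direct contradiction at the first episode requires the further assumption that Grade 1 ends below 5x ULN.

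The main consequence is contradictory stopping instructions, probably for few children. The effect on PFS6 is possible but conditional on timing, on the child's disease status, and on how *off study* is read or whether the 6-month assessment takes place. Where those conditions hold, a single stage-1 child matters in a trial of 23. The design's stated operating characteristics are not in question.

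**What to change.** Reconcile 4.1, 4.2 and 8.1e into one consistent rule set covering recurrence at a reduced dose, by cohort if that is intended, and AST/ALT recovery. State which section governs, and amend the identical-treatment sentence in 4.1 if the cohorts are meant to differ. The clinical content is for the clinical lead; no dose or stopping rule is proposed here.

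Align *off study* in 9.1.1 with 8.1 and 8.2, so that every child removed from therapy for toxicity is scored the same way for PFS6. The cost is amendment wording, with no added procedures and no change to the sample size.

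### After a grade 3-4 fall in blood counts, drug may restart only at grade 1 or less, with no return-to-baseline alternative, although entry accepts counts that are probably worse than grade 1

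*Combined protocol and SAP*

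**What the plan says.** **Entry (3.2.6.1).** The limits apply when the child starts on protocol. For neutrophils the limit is "ANC: $\geq 750/\text{mm}^3$, Must be at least 7 days after last dose of growth factor"; for platelets it is "Platelet Count: $\geq 50,000$ (transfusion independent; ≥ 7 days from last transfusion".

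**Hold and restart (4.2).** AST/ALT has its own numeric rules. Every other grade 3 or 4 toxicity falls under one general rule: "The study drug will be held until resolution of these toxicities to ≤ grade 1". A deadline follows: a child who has not recovered three weeks after her last dose must come off treatment.

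**Removal (8.1 e).** The same test appears among the removal criteria: "Grade 3 or 4 toxicity that does not resolve to Grade 1 within three weeks after interruption of therapy".

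Neither section offers return to baseline or to the entry value as an alternative, and neither treats blood counts separately. Physician judgment (8.1 c) is listed only as a reason to take a child off drug.

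**Grading (10.2).** CTCAE v4.0 is adopted by name; the grade boundaries are not reproduced.

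**The concern.** The count required to resume drug can be higher than the count accepted for the first dose. A child may have a genuine fall on drug, recover completely to where she began, and still have to leave protocol therapy because where she began was already worse than grade 1. The rule is mandatory, and the protocol gives no reason for the difference.

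The liver rule in the same section has no such gap, which suggests that the general rule was not checked against the entry limits. Section 7.0 also favors continuing drug, in the absence of clear progression, for possible late benefit. At stake is an avoidable loss of treatment for a few children.

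**Working it through.** The plan states no figure on this point, so there is none to reproduce. The check sets the rules side by side and then applies assumed cut-points.

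**1. Inputs from the protocol**
- Entry: ANC 750, platelets 50,000 (3.2.6.1).
- Restart: grade 1 or less, within three weeks (4.2, 8.1 e).
- Liver entry: "SGPT (ALT) < 2.5x ULN", and the same for AST (3.2.6.3).
- Liver restart: below 5x ULN after the first episode, below 2.5x ULN after the second (4.2).

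**2. Assumption.** The grade 1 floor is ANC 1,500 (range 1,000-2,000) and platelets 75,000 (range 60,000-100,000).

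**3. Size of the gap.** Ratio = assumed grade 1 floor / entry limit.

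| Count | Assumed floor | Entry band affected | Ratio needed at the entry limit |
|---|---|---|---|
| ANC | 1,000 | 750-999 | 1,000/750 = 1.33 |
| ANC | 1,500 | 750-1,499 | 1,500/750 = 2.00 |
| ANC | 2,000 | 750-1,999 | 2,000/750 = 2.67 |
| Platelets | 60,000 | 50,000-59,999 | 60/50 = 1.2 |
| Platelets | 75,000 | 50,000-74,999 | 75/50 = 1.5 |
| Platelets | 100,000 | 50,000-99,999 | 100/50 = 2.0 |

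A gap exists for any floor above 750 or 50,000. There is none at or below those values, and none for a child who enters at or above the floor.

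**4. Liver rule for comparison.** A child back at her entry value is below 2.5x ULN. That meets both restart limits, so regaining the entry value always permits restart.

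**5. Example courses.** Further assumption: grade 1/2/3 floors are ANC 1,500/1,000/500 and platelets 75,000/50,000/25,000. Each course reads entry, lowest on drug, best within three weeks. The proposed rule is the one given in the fix.

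| Course | Present rule | Proposed rule |
|---|---|---|
| ANC 1,200, 800, 1,200 | off | restart |
| ANC 900, 700, 900 | off | restart |
| ANC 1,200, 800, 800 | off | off (worse grade than Day 1) |
| ANC 990, 510, 700 | off | off (below 750) |
| ANC 1,600, 800, 1,200 | off | off (Day 1 was not worse than grade 1) |
| Platelets 60,000, 40,000, 60,000 | off, unless transfused to grade 1 | restart |
| Platelets 60,000, 40,000, 45,000 | off, unless transfused to grade 1 | off, unless transfused to 50,000 or more |

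**6. How often.** Three things must coincide: a low entry count despite recovery from prior therapy (3.2.5), a grade 3-4 fall on drug, and three weeks without reaching grade 1. The protocol gives no rate for this. Indirect evidence:
- Section 2.3 reports no dose-limiting toxicity in 45 children. The exact one-sided 95% upper limit for 0/45 is 1 - 0.05^(1/45) = 6.4%. Dose-limiting is not defined there and is not the same as grade 3-4, so this is only a guide.
- Section 2.3 reports six grade 2 hematologic events in two adults, with a median duration of five days.
- Section 6.0 describes leukopenia as rare and transient.
- Against this, section 2.2 reports a grade 3 white count (not an ANC) in one of four children with low-grade glioma. It resolved on continued drug.

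**The case against.** **Caution is coherent.** A stable low count at entry differs from a grade 3-4 fall after study drug, and a protocol may reasonably ask for more recovery after the second. This stands as an argument for the hold, and the hold is not disputed. It explains less well why full return to an accepted starting count should end therapy when the liver rule allows restart in that position.

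**The cut-points are not in the documents.** This stands. The size of the gap is conditional, and it vanishes if the grade 1 floors are at or below the entry limits.

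**Platelets may be transfused.** Section 4.3 allows platelet transfusion, at higher thresholds if clinically indicated. Section 4.2 does not repeat the entry requirement of transfusion independence. The platelet case is therefore weaker than the ANC case. Hemoglobin is set aside for the same reason, since 3.2.6.1 itself allows transfusion.

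**Rarity.** This also stands, and it sets the severity.

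A reader might infer three stronger points that the documents do not support:
- *A child entering at ANC 750-999 is held at once, with no change in her count.* This needs a further assumption, that grade 3 begins below 1,000. It also treats an unchanged entry value as a toxicity. Section 4.2 concerns toxicities that resolve, and the Toxicity Evaluation in section 5.0 starts on Day 15.
- *She would then be removed for "recurrent grade 3 or 4 toxicity at a reduced dose level (see section 4.2".* The rule for other toxicities follows the AST/ALT steps. The first restart is therefore at the full 20 mcg/kg, and the reduced dose comes only after a second episode. Reaching it needs two recoveries to grade 1, which is what this child does not achieve. For NF1 children, 4.2 adds a possible restart at 5 mcg/kg.
- *The rule costs power or biases PFS6.* No frequency is available, and follow-up continues after protocol therapy ends (8.1). Whether such a child counts as a failure depends on how the off-study wording in 9.1.1 and the not-assessable wording in 9.1.5 are applied.

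**Conclusion.** The point holds in a limited form. Sections 4.2 and 8.1 e impose a restart standard that a child admitted under 3.2.6.1 may fail even after complete recovery to her entry count, and she must then leave protocol therapy. At the assumed grade 1 floors this concerns entry ANC 750-1,499 and, less firmly, entry platelets 50,000-74,999. At the entry limits the count must reach 2.00 and 1.5 times its starting value (ranges 1.33-2.67 and 1.2-2.0).

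The absence of a baseline alternative is read directly from the text. The size of the gap rests on the assumed floors. The event is probably rare among 23 subjects, and no effect on power, the type I error rate or the primary endpoint is claimed. This is a low-severity, cheap improvement.

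**What to change.** In 4.2 and 8.1 e, replace the single grade 1 condition with: *grade 1 or less or, for hematologic toxicities, return to the Day 1 baseline grade with the count at or above its 3.2.6.1 entry limit*. Keep the three-week window, the grade 3-4 hold for falls on drug, the dose steps (including the 5 mcg/kg step for NF1), and the grade 1 rule for all other toxicities. A total white count has no entry limit in 3.2.6.1, so it would stay under the grade 1 rule.

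**Cost.** One clause in two places. The Day 1 CBC is already drawn, so no test or visit is added.

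**Downside.** A few children would resume at a count worse than grade 1, though never below the limit accepted for a first dose. If grade 3 begins below ANC 1,000, the grade condition does little for a child entering at 750-999; the 750 limit then protects her, and she could resume below her own Day 1 count. After Day 15 the scheduled CBCs come only before each 28-day cycle, so the team may want an unscheduled count after such a restart.
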